#### I. Specific Aims

- 1. Through a mixed-methods process evaluation, assess the feasibility and acceptability of the *¡VMV*! intervention and associated study procedures, as administered in a community-based health service system.
- 2. Preliminarily examine the efficacy of the *¡VMV*! intervention to improve patient-relevant outcomes pertaining to diabetes and CVD risk and general health promotion.
- 3. Based on data collected from Aims 1 and 2, refine and optimize the lifestyle intervention to prepare for a large-scale RCT.

#### **II.** Methods

#### A. Study Design

In the proposed study, 40 Latino adults aged 50-65 years old will be included. All participants will receive the intervention. Throughout the course of their study involvement, participants will continue to receive usual care at their regular primary care facilities or community health clinics or from community-based programs in which they are enrolled.

An assessment battery, consisting of both questionnaire and clinical outcome measures, will be administered at baseline, a subsequent four-month post-testing session, and a 12-month follow-up testing session. Each assessment period will include an in-person assessment to obtain clinical values and responses to questionnaires. Each in-person assessment period is expected to last about 1.5 to 2 hours. In addition to study-generated measures, we will collect electronic data on medical service utilization and clinical assessments from our collaborating healthcare partners. Finally, at the conclusion of the intervention and post-testing, we will collect information about implementation issues, including reach, patient and staff satisfaction, identification of intervention facilitators and barriers, and program sustainability.

Total length of enrollment will include one day for initial testing, four months for the intervention, one day for follow-up testing post-intervention, one day if the person participates in a post-intervention focus group, and one day if the person participates in the 12-month follow-up testing session.

B. Participants, Recruitment, and Consent

2.

A convenience sample of 40 late middle-aged (50-65 years old) Latino adults will be recruited from direct personal contacts at recruitment tables, provider referrals, and postings at the Antelope Valley Community Clinic and local community centers. If a potential participant responds to a flyer and calls a study team member, the screening form will be utilized to describe the study and ensure his/her eligibility. For those individuals who participated in the study as a supervisor, intervener, or tester, research staff will directly approach them to solicit participation in a follow-up interview.

Potential participants for the intervention and follow-up focus group will be included if they:

- 1. Are male or female adults aged at least 50 years at the outset of the four-month intervention and will be no older than 65 years upon completion of the intervention *Justification*: This age group is at high risk for developing disease in older age and likely
  - amenable to an intervention that may help prevent or delay chronic disease in later life Self-identify as Latino/Hispanic
    - *Justification*: The intervention was culturally tailored to and designed for Latino adults. Latino adults are at high risk for certain chronic diseases which could potentially be prevented or delayed through lifestyle intervention
- 3. Are fluent in Spanish Justification: Group sessions will be held in Spanish. Individual sessions may take place in either English or Spanish, depending on the participant's preference
- 4. Live in Antelope Valley and do not plan on moving within six months from the beginning of the study
- 5. Are enrolled as a patient in the Antelope Valley Community Clinic
- 6. Have visited his/her primary care healthcare facility within the past year *Justification*: This criterion ensures that patients are "active" in the health care system
- 7. Will be available by telephone for the duration of the intervention *Justification*: A portion of the intervention is delivered via telephone
- 8. Are oriented to person, place, and time as tested by asking the person's name, date, age, and place of residence
- 9. Self-report their ability to participate for the duration of the intervention

Individuals who participated as supervisors, interveners, or testers will be included for a follow-up interview if they:

1. Held the role of supervising occupational therapist or *promotor*, intervening *promotor*, or tester during study implementation.

After screening, informed consent materials will be sent or handed to prospective participants for pre-review. Only key personnel who are HIPAA and CITI certified, trained in consenting procedures, and do not have a conflict of interest will conduct the consent process. The consenter will explain the study procedures and describe in detail what will be expected of participants. Participants will have ample time to ask questions about the study and their role in it. If the individual is interested in participating, s/he will sign the consent form. If participants are not comfortable with the study, they may choose not to participate.

For the 12-month follow-up testing session, the project manager will mail the Consent Addendum with a cover letter, which will (a) invite existing participants to participate in this additional assessment session; (b) encourage them to read the enclosed consent document; and (c) inform them that the assessor (who is HIPAA and CITI certified) will contact them soon to schedule a time to go over the informed consent, enroll them in the study if they are willing, and complete the assessments if they are willing. The assessor and primary Spanish study contact will call each of the existing participants to schedule a time to go over the informed consent, enroll them in the study if they agree to participate, and complete the assessment battery.

# C. Assessment Procedures

Following the informed consent process, participants will complete a battery of self-report questionnaires and clinical tests. The following data, with the exception of fixed background variables, will be assessed during each measurement point (baseline, four months, and 12 months). Participants may undertake assessment in Spanish or English, as preferred.

*—Background*. Information regarding participants' background and demographics (e.g., sex, race, smoking status, insurance coverage) will be collected using a study-specific questionnaire. Additionally, ongoing health problems will be documented (i.e., a checklist will include selected health conditions such as cancer, heart attack, heart failure, hypertension, high cholesterol, arthritis, asthma, alcohol abuse, drug abuse, mental/psychiatric problem, other).

*—Measure Your Medical Outcome Profile 2* (MYMOP2). The MYMOP2 is a simple patient-centered questionnaire that asks the participant to identify one or two symptoms that are bothersome. Patients rate the severity of the symptoms as well as how much they interfere with their daily activities. Upon retest, participants are asked about the symptoms that were initially identified, but are not told what their initial ratings were. The questionnaire has been shown to be sensitive to change, and has demonstrated construct  and criterion validity. Most importantly, this short item questionnaire gets to the heart of what is important to the patient and measures the personally relevant effect of changes that have taken place over the measurement interval. Therefore, the mean degree of change across the set of self-reported symptoms on the MYMOP2 will be used as the study's secondary outcome.

*—Block 2005 Food Frequency Questionnaire Spanish Version* (Block FFQ). The Block FFQ was designed to estimate usual and customary intake of a wide array of nutrients and food groups. It takes 30-40 minutes to complete and is intended for either self- or interviewer-administration (we intend to use interviewer-administration). The bilingual format, with text in both Spanish and English will be used. This version of the FFQ has additional food items typical of diets among Hispanics. The food list for this questionnaire was developed from NHANES 1999-2002 dietary recall data; the nutrient database was developed from the USDA Food and Nutrient Database for Dietary Studies (FNDDS), version 1.0. A series of "adjustment" questions provide greater accuracy in assessing fat and carbohydrate intake. Individual portion size is asked for each food, and pictures are provided to enhance accuracy of quantification.

*—International Physical Activity Questionnaire* (IPAQ). Exercise will be measured using the long version of the IPAQ. This assessment includes 12 to 27 items, depending on the number of non-applicable questions that the respondent is allowed to skip. The questionnaire contains job-, transportation-, household-, and recreational-related physical activity, and time spent sitting. This questionnaire has been used extensively in varying cultures and has been validated with accelerometer data.

—*Satisfaction with Participation in Discretionary Social Activities* and *Satisfaction with Participation in Social Roles* short forms. These two scales, contained on the Patient Reported Outcomes Measurement Information System (PROMIS), will be used to measure satisfaction with participation. Each covers the past seven days and contains 7 questions answered on a 5-point scale. These short forms, as well as the full Satisfaction with Participation bank, have been extensively tested and validated.

— *PROMIS: Emotional Distress* – *Depression* - *Short Form* 8*a*. This instrument uses 8 items to assess depression over the past seven days. These 8 items have been calibrated and validated in both English and Spanish using Item Response Theory. The short form has the advantage of providing almost as much precision as the full item bank (r=.977), while substantially reducing the testing burden on the participant.

*—Pittsburgh Sleep Quality Index* (PSQI). Sleep quality within a one-month period will be measured using the 19item PSQI. This assessment produces a global sleep quality score and seven subscores: sleep quality, sleep latency, sleep duration, habitual sleep efficiency, sleep disturbance, use of sleeping medications, and daytime dysfunction. This measure has been validated in adult and older adult populations.

*—Clinical Measures*. Non-fasting blood samples will be drawn using finger pricks and the Afinion (HBA1C) and Cholestech (Lipid Test) meters will be used to assess HbAlc and lipid profiles (total, HDL, and LDL cholesterol, and triglycerides). We have chosen to not require participants to fast at the time of blood draw. This will increase patient participation and decrease patient inconvenience. Recent studies have shown minimal difference between fasting and non-fasting values for total, HDL, and LDL cholesterol. Blood pressure will be measured using an average of two readings taken from a digital blood pressure monitor. BMI (weight in kilograms divided by height in meters squared) will be obtained using a standard weight scale and stadiometer. Waist circumference will be measured via tape at the midpoint between the iliac crest and the lower rib. Hip circumference will be measured

via tape at the level of the trochanter and used in the calculation of waist to hip ratio. Elo et al.'s Single Item Stress Index will be used to assess level of stress using a 5-point Likert scale that captures general level of stress "these days." It correlates well (r=0.20-0.75) with other validated measures of mental well-being. Self-reported healthcare utilization will be collected including ER visits, hospitalizations, and clinic visits.

*—Disease Risk Scores*. In response to strong interest in the study population for overall risk scores for CHD and diabetes, we will use the Framingham Risk Score LDL Points Total to measure CHD risk and the EPIC Diabetes Risk Score to measure diabetes risk. Both risk scores are modifiable by lifestyle behaviors and calculable from data that are already being collected during the background and clinical assessment, and thus will not add to the participants' testing burden.

*—Healthcare Service Utilization.* We will extract data from each participant's electronic medical record for routine and preventive healthcare utilization (e.g., number of clinic, lab, and other preventive, diagnostic, or screening visits) and non-routine healthcare utilization (e.g., number of emergency department visits and hospitalizations) during the six months prior to baseline and at the end of the intervention. This extraction process will be conducted by the assessors on the study team.

*—Patient Activation Measure (PAM) 13.* The PAM 13 is a 13-item short form tool that assesses a patient's knowledge of, skills in, and confidence in health self-management. Following assessment, a patient is classified in one of four progressively higher activation categories. This 13-item short form has been validated as a measure of a patient's level of engagement in his/her own healthcare.

*—Brief Pain Inventory (BPI; short form) subscales: Pain Severity and Pain Interference.* The BPI Severity subscale measures the amount of pain a person experiences at its "worst," "least," and "average" severity as well as the pain he/she is in "now." The BPI Interference subscale assesses how much a person's pain interferes with everyday life including general activity, walking, work, mood, life enjoyment, relationships, and sleep. The BPI short-form and its subscales are considered valid and reliable. The Spanish-translated tool has been validated in a Spanish-speaking population.

*—Dietary Habits Questionnaire.* The My Habits questionnaire measures participants' heart-healthy behaviors, consisting of 3 subscales: salt intake, cholesterol and fat consumption, and weight control behaviors. The questionnaire has been shown to be reliable in previous studies with Hispanic adults.

#### D. Intervention Procedures

*—Background.* The intervention is informed by Lifestyle Redesign (LR), a health promotion program which has produced beneficial effects in underserved, ethnically diverse, older minority populations. LR enables patients to design, practice, and ultimately enact a personalized, sustainable health-promoting daily routine that is tailored to address CD risk factors as well as promote health and well-being more generally. *Promotores* – health workers in the Latino community who have completed specialized training to provide basic health education programs – will serve as the front line *¡VMV*! interveners. Typically well-respected in their communities, they are perceived as sharing commonly held values and predisposed to deliver interventions in a culturally sensitive manner.

The American Occupational Therapy Association published the original LR manual in 1999. A second edition was released in April 2015. An investigative team from the United Kingdom has been studying the effectiveness of a LR spinoff adapted to the needs of British elders when implemented in the UK National Health Service system. *¡VMV*! is the first version of the LR program that has been tailored for late middle-aged Latinos with or at risk for CDs.

*—Structural Overview.* The *¡VMV*! intervention is divided into five units representing different content areas and follows the general activity-based, culturally sensitive treatment strategies of other LR interventions. The treatment protocol includes eight 1-hour individual sessions, three 1-hour group sessions, and two 15-minute telephone calls— all delivered over four consecutive months in a tapered design, as outlined in Table 1. Individual sessions, which will occur in patients' homes or in a public location of the patient's choosing, will allow patients to pursue their self-identified goals and to receive personalized health information. Group sessions, which will take place at the Antelope Valley Community Clinic, will be devoted to synthesizing individual session instruction, sharing experiences related to embracing a healthy lifestyle, and problem-solving as a means

of fostering peer support and advisement from other patients. Phone calls will be utilized to maintain contact with patients and to monitor their experience with lifestyle change.

	Month 1	Month 2	Month 3	Month 4	Total
# Individual (in-home) Sessions (1 hour)	3	3	2	0	8
# Group Sessions (1 hour)	1	1	0	1	3
# Telephone Sessions (15 minutes)	0	0	1	1	2
Total contacts	4	4	3	2	13

Table 1: Intervention sequence for one participant

-Content. The five educational units contained in the *iVMV*! manual will be used to organize the presentation of principles and strategies to achieve a healthy and active lifestyle. These units are summarized in Table 2 and include: Healthy Eating and Physical Activity; Healthcare Navigation; Chronic Disease Management; Mental Well-being; and Wrap-up. To promote patient-centeredness, flexibility, and customization, the treatment plan includes standard content for all patients and discretionary content which will be presented to a given patient only when relevant. For example, as a part of the Healthy Eating and Physical Activity unit, all patients will be taught how to incorporate a balance of protein, fruits, vegetables, grains, and oils into meals. However, this unit will also contain discretionary content that pertains to specific diseases (e.g., self-care for diabetes) which will only be presented if appropriate.

Unit	Month	Week	Туре	Title		
	1 (3/1/0)*	1	Ι	Session 1: Introduction		
Healthy Eating & Physical Activity Healthcare Navigation Chronic Disease Mgmt. Mental Well-Being		2	Ι	Session 2: Transform Your Eating Habits Today		
		3	Ι	Session 3: Making Healthy Food Choices in Real-Life		
				Situations (Outing)		
		4	G	Session 4: Healthy Eating in Social Situations		
	2 (3/1/0)	5	Ι	Session 5: Healthy Physical Activity and You		
		6	Ι	Session 6: Getting the Most out of Your Healthcare		
		7	Ι	Session 7: Disease Specific Health Management (Flexible)		
		8	G	Session 8: Gratitude and a Positive Outlook		
		9	Ι	Session 9: Mental Well-Being		
		10	Ι	Session 10: Stressors (Flexible Sessions)		
				Session 10a: Finances and Your Health		
	3			Session 10b Sleep		
	(2/0/1)			Session 10c: Effective Communication		
				
 
Session 10d: Coping with Loss
 
		
				• Session 10e: Safety		
		11	Т	Session 11: Follow-Up		
Wrap-Up	4	12	G	Session 12: Graduation		
	(0/1/1)*		Т	Session 13: Follow-Up		

 
 Table 2: Intervention units and associated sessions
 Tranc

*Notes*: I=Individual; G=Group; T=Telephone

Although at the outset of the intervention patients will be assigned to groups of ten, the first session will be individualized and, in most cases, home-based. In this session, led by both the *promotor* assigned to the patient's group and an occupational therapist who will be present via teleconference using HIPAA compliant VSee software, the patient will be able to review a personalized Health Status Report, which contains a summary of the most recent information extracted from his or her health records, including health markers such as weight and blood pressure levels. After discussing this report, the patient, occupational therapist, and promotor will develop a Health Action Plan (HAP). The HAP will include three health-related goals that the patient wishes to achieve through the intervention and a list of four to five strategies or activities that can be implemented to achieve these goals. Additionally, each participant will be given a wrist-worn activity monitor to keep permanently even after the intervention concludes. Participants will be instructed in the features of the monitor and guided in how they

could use it to help achieve the goals delineated in the HAP, as appropriate. Through ongoing individual and group supervisory meetings, the occupational therapist will use the information from the HAP to guide the *promotor* in tailoring the intervention to meet individual patient's needs.

During the course of individual, group, and phone sessions, the HAP will be updated with topic-specific unit content. At the beginning of month three, the *promotor* will take note of the progress that the patient has made toward his or her goals and reassess various health indicators such as weight or blood pressure. These results will be forwarded to the patient's physician. Concurrently, patients will be encouraged to review these results to self-monitor any change in their health status. By the conclusion of the intervention, each patient will be helped to adopt his or her HAP to maximize the likelihood of lifelong implementation of health-enhancing activity and habits.

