# **III. Statistical Considerations**

# A. Sample Size

We will enroll 40 participants in this pilot study. With this sample size we will have 80% power to detect a statistically significant change score effect size of 0.454 in any of our continuous outcome variables (two-sided alpha=0.05, paired sample t-test). This is considered a medium effect size. In the Well Elderly 2 study, effect sizes were generally small. Therefore, we expect this pilot study to have minimal statistical power. Nevertheless, this sample size is adequate for assessing the feasibility and acceptability of this intervention and to identify any obstacles that need to be addressed before a large-scale version of this study can be undertaken.

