# *Specific Aim 2: Preliminarily examine the efficacy of the ¡VMV! intervention to improve patient-relevant outcomes pertaining to diabetes and CVD risk and general health promotion.*

Efficacy of the intervention will be preliminarily evaluated based on comparison of baseline and post-intervention data collected on the following outcomes: perceived clinical outcomes related to symptoms, activity, and wellbeing (MYMOP2), pain (BPI Pain Severity and Pain Interference subscales), dietary intake (Block Food Frequency Questionnaire), dietary habits (My Habits Scale), self-reported exercise (IPAQ), sleep quality (PSQI), satisfaction with participation (PROMIS Satisfaction with Participation in Discretionary Social Activities and Satisfaction with Participation in Social Roles short forms), depression (PROMIS Emotional Distress -Depression – Short Form 8a), stress (Elo et al.'s Single Item Stress Index), patient activation (PAM-13), clinical outcomes (HbAlc, lipid profiles, waist and hip circumference, waist to hip ratio), CHD risk (Framingham Risk Score LDL Points Total), diabetes risk (EPIC Diabetes Risk Score), and healthcare service utilization.

Data will be directly entered into the Research Electronic Data Capture (REDCap) system. Data will be checked for completeness and reasonableness. Descriptive statistics will be presented and analyses will inform the appropriateness of our intended statistical plan. Changes in outcome variables will be assessed using paired-sample t-tests. Baseline covariates (e.g., age, gender), will be assessed for effect modification. Results will be stratified by any effect modifiers, and repeated measures ANOVA will be used to adjust for confounders. These preliminary estimations will inform refinement of the outcomes assessment battery and sample size calculations for a subsequent large-scale trial.

*Specific Aim 3:* Based on data collected from Aims 1 and 2, refine and optimize the lifestyle intervention to prepare for a large-scale randomized controlled trial.

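### Participants are treated in promotor-assigned groups of ten but sized and tested as 40 independent people; if change correlates within groups, the paired t-test p-values and intervals are too favourable

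*Combined protocol and SAP*

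**What the plan says.** The study has one arm: "All participants will receive the intervention" (II.A), and "We will enroll 40 participants in this pilot study" (III.A).

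On delivery, II.D states: "Although at the outset of the intervention patients will be assigned to groups of ten, the first session will be individualized". The first session is "led by both the *promotor* assigned to the patient's group and an occupational therapist", the latter attending by teleconference. Table 1 gives each participant eight individual sessions, three group sessions and two telephone calls. II.D describes peer support as one purpose of the group sessions.

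On sizing, III.A states: "With this sample size we will have 80% power to detect a statistically significant change score effect size of 0.454", for a two-sided 5% paired t-test. On analysis, III.B (Specific Aim 2) states: "Changes in outcome variables will be assessed using paired-sample t-tests". The further modelling in III.B looks for effect modification by baseline covariates, with age and gender as examples, and uses repeated measures ANOVA to adjust for confounders. Section III does not mention group, promotor, an ICC or a design effect.

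On use of the results, III.B states: "These preliminary estimations will inform refinement of the outcomes assessment battery and sample size calculations for a subsequent large-scale trial".

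**The concern.** A paired t-test on 40 change scores assumes that one person's change says nothing about another's. Here, members of a group share an assigned promotor, who helps write and tailor the action plan, and they meet as a group three times. Peer influence is part of the intended mechanism, so some positive correlation of change within groups is plausible.

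If it exists, the standard error is too small, the intervals are too narrow, and a true null is rejected more often than 5% of the time. A good result in one group could then be read as an effect of the programme as a whole. The same estimates are meant to inform the sample size of the large trial, and the plan does not say that clustering will be considered there.

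**Working it through.** **Inputs.** From III.A: n = 40, two-sided alpha 0.05, paired t-test, standardised change 0.454, power 80%. From II.D: group size 10. Derived: 40/10 = 4 groups, if everyone is grouped and groups are full. Assumed, because the documents give no value: ICC of the change scores 0.01, 0.05 or 0.10.

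**1. The plan's own figure.** Noncentrality = 0.454 × √40 = 2.871 on 39 df, with critical value 2.023. The noncentral t gives power 79.96%, and 80% power corresponds to an effect of 0.4543. The stated figure reproduces, and it is the ICC 0 case.

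**2. Variance of the mean change.** Design effect DE = 1 + (10 − 1) × ICC, and effective n = 40/DE.

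| ICC | DE | Effective n | Standard error multiplier √DE |
|---|---|---|---|
| 0 | 1.00 | 40.0 | 1.00 |
| 0.01 | 1.09 | 36.7 | 1.04 |
| 0.05 | 1.45 | 27.6 | 1.20 |
| 0.10 | 1.90 | 21.1 | 1.38 |

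**3. Type I error of the planned test.** Clustering also slightly lowers the expected sample variance. With total variance 1, its expectation is [3(1 + 9·ICC) + 36(1 − ICC)]/39 = (39 − 9·ICC)/39. At ICC 0.05 this is 38.55/39 = 0.988. The true standard error is then √(1.45/0.988) = 1.211 times the one the test uses, so the effective critical value is 2.023/1.211 = 1.670. On 39 df the two-sided tail area is 10.3%. The same steps give 6.0% at ICC 0.01 and 15.5% at ICC 0.10. Simulation of four groups of ten with the planned t-test agrees: 5.9 to 6.0%, 10.1 to 10.3% and 15.3 to 15.7% across runs, and about 5% at ICC 0.

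**4. Power at 0.454 depends on the test.**

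| ICC | Planned t-test, simulated rejection rate | Effective n, 39 df | Group-mean t-test, 3 df |
|---|---|---|---|
| 0 | 80% | 80% | 50% |
| 0.01 | 79% | 76% | 47% |
| 0.05 | 76% | 64% | 38% |
| 0.10 | 74% | 53% | 31% |

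The first column stays high partly because that test no longer holds its 5% level. The second inflates the variance but keeps 39 df. The third is a valid group-level test, but four groups leave it few degrees of freedom. A power figure means little unless its test is named.

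**5. What four groups can say about the ICC.** For an estimate of 0.05, F = (1 + 9 × 0.05)/(1 − 0.05) = 1.526 on 3 and 36 df. The 95% interval for the ICC is about −0.06 to 0.67.

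**6. Consequence for the randomised trial.** Its design is not described. If individuals were randomised in equal arms with equal variances and only the intervention arm were grouped, with groups again of ten (all assumed), the inflation would be about (1 + DE)/2. That is (1 + 1.45)/2 = 1.23 at ICC 0.05 and (1 + 1.90)/2 = 1.45 at ICC 0.10.

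**The case against.** The strongest defence is that the plan claims little. III.A expects minimal power and justifies 40 participants by feasibility, III.B calls the efficacy look preliminary, and completion of Aim 3 does not depend on significance. Ten of the 13 contacts are individual sessions or calls, and content is personalised, so the correlation may be small. Differences between promotores would partly surface through session notes, fidelity checks, exit interviews and adherence records. All of this stands, and it lowers the severity. It does not remove the point: the power caveat in III.A rests on small effects in an earlier study, and it does not address a standard error that is too small or a type I error above 5%.

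A reader might infer three stronger claims that the documents do not support.

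- *The p-values and the 80% are wrong as they stand.* The documents give no ICC. At ICC 0 both are correct.
- *Each group has a different promotor, so the pilot could estimate differences between operators.* The number of promotores is not stated; II.E uses the plural, which implies at least two. One promotor may lead several groups, and group and promotor effects may not be separable. If two promotores each led two groups and clustering were by promotor (assumed), type I error would be 7.3% at ICC 0.01 and 16.0% at ICC 0.05.
- *The later trial will be undersized by the full design effect.* Its design is not given, and III.B does not say that clustering will be ignored.

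**Conclusion.** The point holds in conditional form. Participants are nested in promotor-assigned groups, and Section III sizes and tests them as independent. For any positive within-group correlation of change, the paired t-test p-values and intervals are too favourable. Over assumed ICCs of 0.01 to 0.10, nominal 5% becomes about 6% to 15%, and standard errors should be about 4% to 38% larger.

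This rests on four full groups of ten (derived), on the assumed ICC range, and on wanting conclusions that reach beyond the particular groups treated. The feasibility aim is not affected. Severity is low, since no decision depends on a p-value, but the correction is cheap and bears on what is carried forward to the randomised trial.

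**What to change.** 1. In III.A, state that 80% power at 0.454 assumes no correlation of change within groups. If figures under clustering are added, name the test they belong to: effective n with 39 df, or a group-mean test on 3 df. State the number of groups and of promotores.
2. In III.B, record group and promotor for every participant. Tabulate mean change and attendance by group beside the pooled result. Label the paired t-test p-values as assuming independence between participants. As a sensitivity analysis, show standard errors multiplied by √DE over a stated ICC range.
3. For the randomised trial, allow for clustering over a stated ICC range, using the inflation that fits its design. Do not rely on an ICC estimated from four groups.

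The cost is a few lines of text, one extra table and stated precision that looks less favourable. Group and promotor should already be known from delivery, so no extra participants or visits are needed.
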